### **3.4. Duration of Treatment**

Randomized subjects will receive a maximum of 58 weeks of study drug. Subjects who are non-responders based on the results of the Week 10 assessments will be offered the option to receive open-label filgotinib by entering into the LTE study (GS-US-419-3896).

Subjects meeting disease worsening criteria at Week 11 or later must be discontinued from blinded treatment and will be offered the option to receive open-label filgotinib in the LTE study (See Section 3.6, Disease Worsening Criteria).

Subjects who complete all procedures per protocol, including the endoscopy of the Week 58 visit, will have the option to continue study drug in a blinded fashion in the LTE study.

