### **3.6. Disease Worsening Criteria**

Subjects meeting the following disease worsening criteria evaluated after Week 11 must be discontinued from blinded treatment and will be offered the option to receive open-label filgotinib by entering into the separate LTE study (GS-US-419-3896).

- Increase in CDAI score  $\geq$  100 points from the Week 10 value and CDAI score  $\geq$  220 points at 2 consecutive visits.
  - The disease worsening visits may include unscheduled visits (eg, a study visit followed by an unscheduled visit, or 2 sequential unscheduled visits anytime subsequent to the Week 11 visit).
- If a subject experiences significant worsening of underlying CD, which requires any of the prohibited medications (refer to Section 5.4.2), or surgical intervention at any point during the study, treatment discontinuation should be considered at investigator's discretion, in consultation with medical monitor if feasible (refer to Section 3.5.2); these subjects do not qualify for LTE study.

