### **Summary of Dichotomous Efficacy Endpoints**

For the Cohort A Induction Study, the Cohort B Induction Study, and the Maintenance Study, numbers and percentages of subjects achieving each of the dichotomous efficacy endpoints defined above, and numbers and percentages of subjects not achieving those endpoints for the following reasons will be summarized by treatment, in a hierarchy order with the first reason being the highest.

- 1) Data censored due to initiation or change of rescue medication
- 2) Subjects who do not meet the endpoint based on observed data
- 3) Subjects who do not meet the endpoint due to study drug discontinuation led by protocol-specified disease worsening (Maintenance Study only)
- 4) Subjects who do not have sufficient measurements to determine the endpoint due to study drug discontinuation for other reasons
- 5) Subjects who do not have sufficient measurements to determine the endpoint for other reasons

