##### Maintenance Study

- Any AEs with an onset date on or after the study drug start date for the Maintenance Study and no later than 30 days after last dosing date of Maintenance Study
- Any AEs leading to premature discontinuation of Maintenance Study drug

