##### 7.1.6.1. Summaries of AE Incidence

The number and percentage of subjects who experienced at least 1 TEAE will be provided and summarized by SOC, HLT, PT, and treatment group. For other AEs described below, summaries will be provided by SOC, PT, and treatment group:

- TEAEs of Grade 3 or higher (by maximum severity)
- TEAEs of Grade 2 or higher (by maximum severity)
- All TE treatment-related AEs
- TE treatment-related AEs of Grade 3 or higher (by maximum severity)

- TE treatment-related AEs of Grade 2 or higher (by maximum severity)
- All TE SAEs
- All TE treatment-related SAEs
- All TEAEs leading to premature discontinuation of study drug
- All TEAEs leading to premature discontinuation of study
- All TE SAEs leading to death (ie, outcome of death)
- All TEAEs leading to temporary dose interruption of study drug

A brief, high-level summary of AEs described above will be provided by treatment group presenting the number and percentage of subjects who reported the above AEs. All deaths observed in the study will be also included in this summary.

Multiple events will be counted only once per subject in each summary. Adverse events will be summarized and listed first in alphabetic order of SOC and HLT within each SOC (if applicable), and then by PT in descending order of total frequency within each SOC. In addition, a summary of all AEs occurring at least 2% of subjects will be summarized by SOC and PT in order of descending frequency. For summaries by severity grade, the most severe grade will be used for those AEs that occurred more than once in an individual subject during the study.

In addition, the following tables will be generated and summarized by PT only, in descending order of total frequency:

- TEAEs
- TEAEs of Grade 3 or higher
- TEAEs of Grade 2 or higher
- TE SAEs
- TE treatment-related AEs
- TE treatment-related SAEs
- TEAEs leading to premature discontinuation of study drug

Data listings will be provided for the following:

- All AEs, indicating whether the event is treatment-emergent
- All AEs of Grade 3 or higher
- All AEs of Grade 2 or higher
- SAEs
- Deaths
- All AEs leading to death (ie, outcome of death)
- AEs leading to premature discontinuation of study drug
- AEs leading to premature discontinuation of study
- AEs leading to dose temporary interruption of study drug
- AEs related to COVID-19, as determined by the COVID-19 Standardised MedDRA Query (SMQ) narrow search

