#### **7.1.7. Adverse Events of Interest**

Adverse events of interest (AEI) include infections, malignancies (excluding nonmelanoma skin cancers), nonmelanoma skin cancers, gastrointestinal perforations, major adverse cardiovascular events (MACE), and thromboembolic events. Summaries of the following treatment-emergent AEI will be produced to enhance the analysis of safety data.

- Events of infections, presented in the following subcategories:
  - AEs of infections, utilizing all AEs in the MedDRA Infections and Infestations SOC
  - AEs of serious infections, using all AEs in the MedDRA Infections and Infestations SOC that are classified as SAEs
  - AEs of herpes zoster, utilizing an MST list developed by the Sponsor
  - AEs of opportunistic infections (SMQ), utilizing a narrow scope PTs

- AEs of malignancies, excluding nonmelanoma skin cancers, utilizing an MST list developed by the Sponsor
- AEs of nonmelanoma skin cancers, utilizing an MST list developed by the Sponsor
- AEs of gastrointestinal perforations, utilizing an MST list developed by the Sponsor
- AEs of MACE, utilizing a positively adjudicated event list, presented in the following subcategories (Section 7.1.7.1):
  - Cardiovascular (CV) death
  - Non-fatal myocardial infarction (MI)
  - Non-fatal stroke
- AEs of arterial systemic thromboembolism (ASTE), utilizing a positively adjudicated event list (Section 7.1.7.1)
- AEs of venous thromboembolism (VTE), utilizing a positively adjudicated event list (Section 7.1.7.1)

A list of all AE PTs is provided in Appendix 9.

The number and percentage of subjects with a reported event will be summarized for each treatment group by PT for each AEI category. A data listing for each category of AEI will also be provided.

A by-subject listing for subjects with potential events for adjudication. For each AE, it will be described if the AE was adjudicated for a specific category (cardiovascular death, myocardial infarction, stroke, arterial systemic thromboembolism and venous thromboembolism) and their respective adjudication results (NA if not adjudicated for a specific category) will be provided.

A by-subject listing of thromboembolic history and risk factors will be provided for subjects with potential events for adjudication (MACE, ASTE, and VTE).

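### Maintenance adverse events are summarised only as crude percentages although time at risk depends on staying on blinded drug; exposure-adjusted rates should be added beside them

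*SAP*

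**What the plan says.** **Measure.** SAP 7.1.6.1 states: "The number and percentage of subjects who experienced at least 1 TEAE will be provided and summarized by SOC, HLT, PT, and treatment group". The other adverse event tables, including SAEs and events leading to discontinuation, are also subject counts, and "Multiple events will be counted only once per subject in each summary". For infections, malignancy, gastrointestinal perforation, MACE and thromboembolism, SAP 7.1.7 states: "The number and percentage of subjects with a reported event will be summarized for each treatment group by PT for each AEI category". Under SAP 3, Maintenance safety data are shown by induction dose and the maintenance dose that followed. Subjects who stay on filgotinib therefore stand beside those re-randomized to placebo.

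**Window.** Under SAP 7.1.5.1 a Maintenance event counts from the first Maintenance dose to "no later than 30 days after last dosing date of Maintenance Study".

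**Stopping rule.** Under Protocol 3.6, subjects who worsen "must be discontinued from blinded treatment and will be offered the option to receive open-label filgotinib" in the separate extension study. The SAP expects such exits: section 6.1 has a Maintenance-only non-response category for discontinuation due to worsening.

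**Exposure.** SAP 4.2.1 tabulates duration of exposure by treatment group, with cumulative counts to 47 weeks. No person-time denominator, incidence rate or time-to-event summary is planned for any adverse event.

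**The concern.** The chance that a subject is counted in a crude percentage grows with the time over which that subject is observed. Here that time ends with the last dose plus 30 days, and the last dose comes earlier for subjects whose disease worsens. The placebo arms consist of filgotinib responders withdrawn from drug. If filgotinib maintains response, they will tend to worsen and leave sooner. The arms are then compared on a measure that depends on follow-up, when follow-up itself depends on treatment.

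The safety reading of the 47-week phase is at stake. With equal underlying rates, filgotinib could show the higher percentage. A real excess could also be dismissed as an exposure effect, because the planned tables do not separate the two. Protocol 1.4 expects JAK inhibition to raise infection risk, so readers will look closely at these columns.

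**Working it through.** **1. The plan's own figure.** The plan gives no adverse event rate, discontinuation rate or person-time. The nearest figure is the Maintenance power (SAP 1.3): 60 placebo v 120 filgotinib 200 mg, 20% v 50% success, two-sided 0.05, with 94% as the product of two endpoint powers.
- Pooled normal approximation: 0.9842² = 0.969.
- With continuity correction: 0.9755² = 0.952.
- Fisher's exact test: 0.9784² = 0.957.

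The last two come within 2 points of 94%, so the planning rates are read as intended.

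**2. Inputs.**
- From the documents: T = 47 weeks (SAP 4.2.1); tail F = 30/7 = 4.29 weeks (SAP 7.1.5.1); Week 58 failure of 80% on placebo and 50% on filgotinib 200 mg (one minus the rates in SAP 1.3).
- Assumed: a share f of failures leaves blinded drug early, with exponential leaving times; first events occur at the same constant rate in both arms (0.05, 0.2 or 1.0 per person-year; λ = rate/52.18 per week); every subject has the full 30-day tail.

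**3. Formulas.** With q the proportion who leave by week 47 (f × 0.8 or f × 0.5):
- leaving hazard g = −ln(1−q)/T
- mean time at risk = q/g + F
- crude percentage = 1 − e^(−λF) × [g + λe^(−(g+λ)T)]/(g+λ)

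**4. One case in full: f = 1, 0.2 per person-year (λ = 0.003833).**
- Placebo: g = 1.6094/47 = 0.03424. Mean time at risk = 0.8/0.03424 + 4.29 = 27.6 weeks. Crude = 1 − 0.9837 × 0.9161 = 9.9%.
- Filgotinib: g = 0.6931/47 = 0.01475. Mean time at risk = 0.5/0.01475 + 4.29 = 38.2 weeks. Crude = 1 − 0.9837 × 0.8799 = 13.4%.
- Ratio 1.36, although the true rates are equal.

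**5. All cases (placebo v filgotinib).**

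| f | Mean weeks at risk | Crude %, 0.05/PY | Crude %, 0.2/PY | Crude %, 1.0/PY | Crude risk ratio |
|---|---|---|---|---|---|
| 0 | 51.3 v 51.3 | 4.8 v 4.8 | 17.8 v 17.8 | 62.6 v 62.6 | 1.00 |
| 0.25 | 46.4 v 48.3 | 4.3 v 4.5 | 16.2 v 16.8 | 57.7 v 59.6 | 1.03–1.04 |
| 0.5 | 41.1 v 45.1 | 3.9 v 4.2 | 14.4 v 15.8 | 52.3 v 56.4 | 1.08–1.10 |
| 0.75 | 35.1 v 41.8 | 3.3 v 3.9 | 12.4 v 14.7 | 46.1 v 53.0 | 1.15–1.19 |
| 1 | 27.6 v 38.2 | 2.6 v 3.6 | 9.9 v 13.4 | 38.3 v 49.4 | 1.29–1.38 |

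For infrequent events the ratio approaches the ratio of mean times at risk (38.2/27.6 = 1.38 at f = 1). The largest absolute gap is about 11 points. A first-event rate per person-time has ratio 1.00 in every row, by construction.

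**The case against.** **The tables are descriptive, and exposure is shown.** SAP 7.1.6 plans no testing, SAP 4.2.1 shows exposure by group and SAP 4.1 gives reasons for stopping. A reader would see an imbalance and could approximate rates. That stands, but it reveals the problem without correcting the percentages, which readers will compare with or without a p-value.

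**Pooled safety is deferred.** SAP 7.7 leaves the combined Induction-plus-Maintenance analysis to an integrated plan whose content is not given. One therefore cannot conclude that the programme lacks exposure-adjusted rates. The deferral does not cover the Maintenance-only tables, which SAP 7.1.6 keeps here.

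**Direction is not certain.** Protocol 7.1.1 allows complications of lack of efficacy, and pre-existing events that increase in severity, to count as adverse events. Worsening on placebo can therefore add events and offset the shorter follow-up for overall TEAEs. Mandatory stops for serious infection, thromboembolism or laboratory findings (Protocol 3.5.2) could shorten filgotinib exposure if those events are drug-related. Both points stand.

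**Large f is unlikely.** Worsening requires a CDAI rise of at least 100 points and a score of at least 220 at two consecutive visits. Many Week 58 failures will not meet that. This stands.

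**Rates have their own bias.** Suppose both arms have hazard 0.04 per week for 10 weeks and 0.01 after that, with assumed follow-up of 40 weeks (filgotinib) and 30 weeks (placebo). The crude risks are 1−e^(−0.7) = 50.3% and 1−e^(−0.6) = 45.1%, ratio 1.12. The first-event rate ratio is 0.89. Neither measure is neutral when events cluster early, which is a reason to show both.

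**Very rare events stay imprecise.** At an assumed 0.5 per 100 person-years and full follow-up, 120 subjects give 120 × 51.3/52.18 × 0.005 = 0.59 expected events, and 60 subjects give 0.29. No denominator resolves that.

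**Conclusion.** The point holds as a gap in the Maintenance safety summaries. Percentages are the only planned measure, the counting window shortens with early stopping, and one stopping rule is tied to loss of efficacy. If placebo time at risk is shorter, which is likely if filgotinib works as planned, equal rates could appear as a filgotinib excess. Within the model the crude risk ratio is 1.00 to 1.38, and 1.08 to 1.10 if half the failures leave early. These are illustrations. They rest on the 200 mg planning rates, exponential leaving, constant equal hazards and an assumed f; f = 1 is the upper bound of this model.

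A reader might infer more: that equal rates will show as an excess, that placebo subjects may have only half the exposure, that the arms cannot be compared on events of interest, or that rates should replace percentages. The documents do not support these readings. They give no discontinuation rate. Even f = 1 gives 38.2 v 27.6 weeks and about 11 points. Offsetting events are possible, and rates carry a constant-hazard assumption. Efficacy conclusions are untouched. Induction, at about 10 to 11 weeks with no worsening rule, is little affected.

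**What to change.** In SAP 7.1.6.1 and 7.1.7, for the Maintenance Study only:
- Keep the number and percentage of subjects.
- Beside them, add subjects with a first event per 100 person-years at risk, with 95% CI, for TEAEs, SAEs, TEAEs leading to discontinuation of study drug, and each category of interest.
- Define time at risk from the first Maintenance dose to the first event or, if there is none, the end of the last-dose-plus-30-days window. State how the 30-day tail is handled for subjects who enter the extension study, since Protocol 6.5 exempts them from the post-treatment visit and they may already be on open-label drug.
- State the constant-hazard assumption, and that percentages and rates are to be read together.

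Protocol 3.4 applies the worsening rule as "Subjects meeting disease worsening criteria at Week 11 or later must be discontinued from blinded treatment", while Protocol 3.6 reads "Subjects meeting the following disease worsening criteria evaluated after Week 11 must be discontinued from blinded treatment". The two start points differ and should be reconciled.

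The cost is a few extra tables. First and last Maintenance dosing dates are already derived (SAP 3.8.1.2 and 4.2.1), so no new data collection is needed.

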#### **7.1.7. Adverse Events of Interest**

Adverse events of interest (AEI) include infections, malignancies (excluding nonmelanoma skin cancers), nonmelanoma skin cancers, gastrointestinal perforations, major adverse cardiovascular events (MACE), and thromboembolic events. Summaries of the following treatment-emergent AEI will be produced to enhance the analysis of safety data.

- Events of infections, presented in the following subcategories:
  - AEs of infections, utilizing all AEs in the MedDRA Infections and Infestations SOC
  - AEs of serious infections, using all AEs in the MedDRA Infections and Infestations SOC that are classified as SAEs
  - AEs of herpes zoster, utilizing an MST list developed by the Sponsor
  - AEs of opportunistic infections (SMQ), utilizing a narrow scope PTs

- AEs of malignancies, excluding nonmelanoma skin cancers, utilizing an MST list developed by the Sponsor
- AEs of nonmelanoma skin cancers, utilizing an MST list developed by the Sponsor
- AEs of gastrointestinal perforations, utilizing an MST list developed by the Sponsor
- AEs of MACE, utilizing a positively adjudicated event list, presented in the following subcategories (Section 7.1.7.1):
  - Cardiovascular (CV) death
  - Non-fatal myocardial infarction (MI)
  - Non-fatal stroke
- AEs of arterial systemic thromboembolism (ASTE), utilizing a positively adjudicated event list (Section 7.1.7.1)
- AEs of venous thromboembolism (VTE), utilizing a positively adjudicated event list (Section 7.1.7.1)

A list of all AE PTs is provided in Appendix 9.

The number and percentage of subjects with a reported event will be summarized for each treatment group by PT for each AEI category. A data listing for each category of AEI will also be provided.

A by-subject listing for subjects with potential events for adjudication. For each AE, it will be described if the AE was adjudicated for a specific category (cardiovascular death, myocardial infarction, stroke, arterial systemic thromboembolism and venous thromboembolism) and their respective adjudication results (NA if not adjudicated for a specific category) will be provided.

A by-subject listing of thromboembolic history and risk factors will be provided for subjects with potential events for adjudication (MACE, ASTE, and VTE).

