**Malignancies, Excluding Nonmelanoma Skin Cancers - Galapagos Search Term List**

**MedDRA Version 25.0**

TERM_CODE	TERM_NAME	TERM_TYPE
10008965	Chronic lymphocytic leukaemia stage 2	PT
10008966	Chronic lymphocytic leukaemia stage 3	PT
10008967	Chronic lymphocytic leukaemia stage 4	PT
10009013	Chronic myeloid leukaemia	PT
10009014	Chronic myeloid leukaemia (in remission)	PT
10009018	Chronic myelomonocytic leukaemia	PT
10009019	Chronic myelomonocytic leukaemia (in remission)	PT
10009252	Clear cell endometrial carcinoma	PT
10009253	Clear cell sarcoma of the kidney	PT
10009944	Colon cancer	PT
10009952	Colon cancer recurrent	PT
10009953	Colon cancer stage I	PT
10009954	Colon cancer stage II	PT
10009955	Colon cancer stage III	PT
10009956	Colon cancer stage IV	PT
10010030	Colorectal cancer recurrent	PT
10010032	Colorectal cancer stage I	PT
10010033	Colorectal cancer stage II	PT
10010034	Colorectal cancer stage III	PT
10010035	Colorectal cancer stage IV	PT
10010038	Colorectal carcinoma stage 0	PT
10011548	CSF lymphocyte count abnormal	PT
10011549	CSF lymphocyte count increased	PT
10011683	Cutaneous T-cell lymphoma stage IV	PT
10012818	Diffuse large B-cell lymphoma	PT
10012821	Diffuse large B-cell lymphoma recurrent	PT
10012822	Diffuse large B-cell lymphoma refractory	PT
10012823	Diffuse large B-cell lymphoma stage I	PT
10012824	Diffuse large B-cell lymphoma stage II	PT
10012825	Diffuse large B-cell lymphoma stage III	PT
10012826	Diffuse large B-cell lymphoma stage IV	PT
10014720	Endometrial adenocarcinoma	PT
10014733	Endometrial cancer	PT
10014734	Endometrial cancer metastatic	PT
10014736	Endometrial cancer recurrent	PT

GLPG0634-CL-MACE, 20DEC22:15:49

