**Malignancies, Excluding Nonmelanoma Skin Cancers - Galapagos Search Term List**

**MedDRA Version 25.0**

TERM_CODE	TERM_NAME	TERM_TYPE
10062122	Testicular choriocarcinoma	PT
10062123	Testicular embryonal carcinoma	PT
10062124	Testicular seminoma (pure)	PT
10062142	Spleen scan abnormal	PT
10062194	Metastasis	PT
10062195	Metastases to biliary tract	PT
10062196	Metastases to gastrointestinal tract	PT
10062197	Metastases to soft tissue	PT
10062485	Retroperitoneal neoplasm metastatic	PT
10062489	Leukaemia recurrent	PT
10062878	Gastrooesophageal cancer	PT
10062904	Hormone-refractory prostate cancer	PT
10063157	Metastatic glioma	PT
10063523	Colon cancer stage 0	PT
10063536	Vulvar adenocarcinoma	PT
10063569	Metastatic squamous cell carcinoma	PT
10063609	Porocarcinoma	PT
10063616	Radiotherapy to lymph nodes	PT
10063620	Acute lymphocytic leukaemia recurrent	PT
10063693	Malignant neoplasm of eyelid	PT
10063706	Malignant melanoma of eyelid	PT
10063908	Non-Hodgkin's lymphoma unspecified histology aggressive	PT
10063916	Metastatic gastric cancer	PT
10064055	Lip squamous cell carcinoma	PT
10064099	Oropharyngeal cancer stage IV	PT
10064344	Lymphoma transformation	PT
10064581	Desmoplastic small round cell tumour	PT
10064605	Sezary cells increased	PT
10064912	Malignant transformation	PT
10065039	Plasmablastic lymphoma	PT
10065305	Cancer in remission	PT
10065349	Vaginal adenocarcinoma	PT
10065430	HER2 positive breast cancer	PT
10065443	Malignant glioma	PT
10065852	CNS germinoma	PT

GLPG0634-CL-MACE, 20DEC22:15:49

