**Nonmelanoma Skin Cancers - Galapagos Search Term List**

**MedDRA Version 25.0**

TERM_CODE	TERM_NAME	TERM_TYPE
10004146	Basal cell carcinoma	PT
10004178	Basosquamous carcinoma	PT
10004179	Basosquamous carcinoma of skin	PT
10006059	Bowen's disease	PT
10007390	Carcinoma in situ of skin	PT
10011677	Cutaneous T-cell lymphoma	PT
10011678	Cutaneous T-cell lymphoma recurrent	PT
10011679	Cutaneous T-cell lymphoma refractory	PT
10011680	Cutaneous T-cell lymphoma stage I	PT
10011681	Cutaneous T-cell lymphoma stage II	PT
10011682	Cutaneous T-cell lymphoma stage III	PT
10023284	Kaposi's sarcoma	PT
10023286	Kaposi's sarcoma AIDS related	PT
10023288	Kaposi's sarcoma classical type	PT
10023347	Keratoacanthoma	PT
10029266	Neuroendocrine carcinoma of the skin	PT
10037732	Queyrat erythroplasia	PT
10039495	Sarcoma of skin	PT
10040808	Skin cancer	PT
10041823	Squamous cell carcinoma	PT
10041834	Squamous cell carcinoma of skin	PT
10057070	Dermatofibrosarcoma protuberans	PT
10063609	Porocarcinoma	PT
10064755	Atypical fibroxanthoma	PT
10068784	Sebaceous carcinoma	PT
10069680	Eccrine carcinoma	PT
10072891	Skin angiosarcoma	PT
10073087	Malignant sweat gland neoplasm	PT
10073088	Hidradenocarcinoma	PT
10075614	Pilomatrix carcinoma	PT
10076248	Marjolin's ulcer	PT
10079945	Cutaneous lymphoma	PT
10080660	Trichoblastic carcinoma	PT
10081136	Skin squamous cell carcinoma recurrent	PT
10085518	Cutaneous B-cell lymphoma	PT

GLPG0634-CL-MACE, 20DEC22:15:49

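### Porocarcinoma is in both malignancy search lists, and the malignancy list counts test, procedure and vascular terms without confirmation

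*SAP*

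**What the plan says.** SAP Section 7.1.7 (Adverse Events of Interest) sets up two categories side by side. One is "AEs of malignancies, excluding nonmelanoma skin cancers, utilizing an MST list developed by the Sponsor"; the other is "AEs of nonmelanoma skin cancers, utilizing an MST list developed by the Sponsor". The term lists are printed in SAP Appendix 9 (MedDRA version 25.0).

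The same section says how the lists are used: "The number and percentage of subjects with a reported event will be summarized for each treatment group by PT for each AEI category". Each category also has its own listing of events.

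SAP Section 7.1.7.1 sends potential major cardiovascular and thromboembolic events to a blinded adjudication committee. Neither document gives a review, confirmation or precedence rule for malignancy terms. SAP Section 7.1.6 plans no formal testing of adverse events.

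**The concern.** Two categories, one of which is named as excluding the other, should share no term. When the lists alone decide who is counted, an error in a list becomes an error in the table. A term in both lists puts a subject into a category that by name leaves that subject out. A term that describes a test result or an operation puts a subject into a cancer category without a cancer diagnosis.

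Protocol Section 1.4 notes that malignancy has been reported in subjects on filgotinib, and it names lymphoid tissue as a target organ in animal studies. Readers will therefore look at the malignancy count, and non-specific lymphoid findings are an awkward kind of term to have in it.

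**Working it through.** No power or error-rate figure is involved. The check compares the lists term by term.

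**1. Overlap.** The nonmelanoma skin cancer list has 35 distinct preferred-term codes. Compared with the malignancy list, exactly one code is shared: 10063609, "Porocarcinoma".

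**2. Does anything stop it being counted in both categories?** The rule in SAP Section 7.1.6.1 that a subject counts once applies within each summary. It does not act across two categories, and Section 7.1.7 gives no order of precedence between them. The subject would appear in both.

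**3. Terms in the malignancy list that are not a cancer diagnosis.**
- Abnormal tests, nine terms: Aspiration bone marrow abnormal (10003506), Biopsy bone marrow abnormal (10004738), Biopsy lymph gland abnormal (10004798), CSF lymphocyte count abnormal (10011548), "CSF lymphocyte count increased" (10011549), Scan bone marrow abnormal (10053504), Biopsy spleen abnormal (10059227), Lymphocyte morphology abnormal (10062047) and Spleen scan abnormal (10062142).
- Procedures, two terms: Lymphoid tissue operation (10052975) and Radiotherapy to lymph nodes (10063616).
- A vascular term: Thrombophlebitis migrans (10043581), which also stands in the CV Events list of Appendix 9.

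That is 9 + 2 + 1 = 12 terms at least. The CV Events list is broad too, but it only selects events for adjudication. The malignancy list feeds the count directly.

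**4. How skin cancers are divided between the lists.** The skin cancer list holds cutaneous T-cell lymphoma unspecified, recurrent, refractory and stages I to III (codes 10011677 to 10011682; for example "Cutaneous T-cell lymphoma stage III"). The malignancy list holds "Cutaneous T-cell lymphoma stage IV" (10011683). The split is six terms to one. The skin cancer list also has Cutaneous lymphoma, "Cutaneous B-cell lymphoma" and three Kaposi's sarcoma terms. Skin lymphoma and Kaposi terms together are 8 + 3 = 11 of 35 (31%).

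Other skin cancers are divided in a similar way:

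| Skin cancer list | Malignancy list |
|---|---|
| Skin cancer | Skin cancer metastatic |
| Basal cell carcinoma | Basal cell carcinoma metastatic |
| Squamous cell carcinoma of skin | Skin squamous cell carcinoma metastatic |
| Dermatofibrosarcoma protuberans | Dermatofibrosarcoma protuberans metastatic |

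**5. Size of one misplaced subject.** Using planned group sizes (Protocol Section 8.9):
- induction arm: 1/220 = 0.45 percentage points
- maintenance filgotinib group: 1/120 = 0.83 percentage points
- maintenance placebo group: 1/60 = 1.67 percentage points

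**The case against.** The strongest reply is that little of this can happen in practice.

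- **Procedures.** Protocol Section 7.1.1 says that procedures are not adverse events and that the underlying condition is reported instead. The procedure terms should therefore rarely arise.
- **Laboratory and imaging findings.** Protocol Section 7.5 says that laboratory abnormalities are usually not recorded as adverse events, and that a diagnosis replaces the result when there is one. No CSF test or spleen scan appears in the unredacted parts of the protocol's laboratory and procedures tables. This narrows the route but does not close it. The same section requires recording of abnormalities that need intervention or lead to interruption of study drug, and of abnormal assessments with symptoms that meet the definition of an adverse event. Thrombophlebitis migrans is neither a test nor a procedure, so these rules do not keep it out.
- **Visibility.** Tables are by preferred term and each category has a listing, so an odd term would be seen. That helps a careful reader, but the subject is still in the category.

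A reader might infer that porocarcinoma is counted twice in one total. The plan does not support that: the two categories are summarised separately and Section 7.1.7 specifies no combined total. The defect is membership of a category that excludes the term by name.

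A reader might also infer that early-stage skin lymphomas and Kaposi's sarcoma are misfiled. Neither document defines nonmelanoma skin cancer. The list is consistent with a literal reading (cancers of the skin other than melanoma), and the stage IV split fits the pattern in the table above, where advanced disease goes to the malignancy list. Protocol exclusion criteria 19 and 20 do treat lymphoma apart from nonmelanoma skin cancer, but they govern eligibility and not adverse event categories. What remains is that the pattern is inferred and nowhere stated, and it does not explain the porocarcinoma duplicate.

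**Conclusion.** The point holds as a small error in lists that are applied as written. One term is in both lists, and at least 12 terms that are not cancer diagnoses would enter the malignancy category if reported as adverse events. The placement of skin lymphomas and Kaposi's sarcoma calls for a stated rule; it is not shown to be an error.

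The effect is confined to descriptive counts by arm within Cohort A, Cohort B and the Maintenance Study. No test and no efficacy result depends on it. The documents give no malignancy rate, so the number of affected subjects cannot be calculated, and it would be a guess to say what share of the malignancy total one event would be. The percentages for one subject assume that arms reach their planned size. The planned total of 1320 subjects is not the denominator here, because SAP Section 7.7 drops the overall induction-plus-maintenance safety analysis from this study. The expected number of affected events is very small. The case for acting is that the correction costs almost nothing.

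**What to change.** Before the blind is broken for the final analysis, amend SAP Appendix 9 and add one or two sentences to SAP Section 7.1.7:

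1. Keep porocarcinoma in the nonmelanoma skin cancer list only, and state that the two lists are mutually exclusive.
2. Remove the abnormal-test, procedure and vascular terms from the malignancy count. Alternatively, keep them as a search aid and count a subject only after blinded medical confirmation of a malignancy.
3. State the rule that assigns skin cancers to one list or the other, including cutaneous lymphoma by stage and Kaposi's sarcoma, and check both lists against it.

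The cost is an edit to two term lists and a short rule. No new data are needed. Item 2 adds a brief blinded review only if such a term is reported and the sponsor chooses to keep it.
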